8.6.2. Analyses of Secondary Endpoints

Continuous secondary endpoints will be summarized using conventional descriptive statistics (n, mean, standard deviation, median, Q1, Q3, minimum, and maximum) by treatment group and overall. A Wilcoxon rank sum test may be used to compare the treatment groups, in an exploratory manner.

Categorical secondary endpoints will be summarized by number and percentage of subjects that meet the endpoint. A two-sided Mantel-Haenszel test, controlling for the randomization strata, may be used to compare the treatment groups, in an exploratory manner. Missing data will be handled by the missing = failure approach except for the endpoints of HBV DNA \geq 20 IU/mL and HBV DNA \leq 20 IU/mL.

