6.2. Secondary Efficacy Endpoints

6.2.1. Definition of Secondary Efficacy Endpoints

The secondary efficacy endpoints are:

- The proportion of subjects with HBV DNA ≥ 20 IU/mL (as determined by the modified US FDA-defined snapshot algorithm) at Week 96
- The proportion of subjects with HBV DNA < 20 IU/mL and target detected/not detected (ie, < LLOD) at Weeks 48 and 96
- The proportion of subjects with HBeAg loss and proportion with seroconversion to anti-HBe at Weeks 48 and 96
- The proportion of subjects with HBsAg loss and proportion with seroconversion to anti-HBs at Weeks 48 and 96
- The proportion of subjects with normal ALT and proportion with normalized ALT (by central laboratory and AASLD criteria) at Weeks 48 and 96
- The change from baseline in fibrosis as assessed by FibroTest at Weeks 48 and 96

For the final analysis, the following definitions will be used:

- HBsAg loss is defined as HBsAg test result changes from HBsAg positive at baseline to HBsAg negative at a postbaseline visit with baseline HBsAb negative or missing.
- HBeAg loss is defined as HBeAg test result changes from HBeAg positive at baseline to HBeAg negative at a postbaseline visit with baseline HBeAb negative or missing.
- HBsAg seroconversion is defined as HBsAg loss and HBsAb test result changes from HBsAb negative or missing at baseline to HBsAb positive at a postbaseline visit.
- HBeAg seroconversion is defined as HBeAg loss and HBeAb test result changes from HBeAb negative or missing at baseline to HBeAb positive at a postbaseline visit.
- ALT normalization is defined as ALT > ULN (by central laboratory normal range or 2018 AASLD normal range) at baseline but within normal range at a postbaseline visit.

Both baseline and postbaseline borderline serology results will be imputed using the following rules:

- HBsAg and HBeAg borderline will be considered as HBsAg positive and HBeAg positive.
- HBsAb and HBeAb borderline will be considered as HBsAb negative and HBeAb negative.

For the above definitions, baseline will be replaced with open-label baseline for the analyses of subjects in the Open-Label FAS, and with TFFU baseline for the analyses of subjects in the TFFU FAS.

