6.2.2. Analysis Methods for Secondary Efficacy Endpoints

The primary analysis of the proportion of subjects in the Full Analysis Set with HBV DNA ≥ 20 IU/mL (as determined by the modified US FDA-defined snapshot algorithm {U. S. Department of Health and Human Services 2015}) will be repeated for the Week 96 endpoint using the FAS. The Week 96 analysis window is defined as from Study Day 589 to Study Day 840, inclusive.

The analyses for the other secondary efficacy endpoints will be conducted using the FAS. All secondary efficacy endpoints involving proportions will be analyzed from baseline to Week 96 using both the Missing Failure (M F) approach and the Missing Excluded (M E) approach, unless otherwise specified. In the M E approach, all missing data will be excluded in the computation, and in the M F approach, all missing data will be treated as failures and included in both the numerator and denominator. P-values will be calculated using the CMH test stratified by baseline HBeAg status (HBeAg-positive or HBeAg-negative) and age (< 50 or ≥ 50 years), and the proportion difference between the 2 treatment groups and the associated 95% CIs will be calculated based on the stratum-adjusted MH proportion.

The change from baseline in \log_{10} (HBsAg) (IU/mL), both overall and by baseline HBeAg status, and ALT will be summarized by visit using observed data (ie, missing data will be excluded). The p-value, differences in change from baseline in \log_{10} (HBsAg) (IU/mL) and ALT between the 2 treatment groups and the associated 95% CI will be constructed using analysis of variance (ANOVA) models, including treatment group, baseline HBeAg status (HBeAg-positive or HBeAg-negative), and age (< 50 or \geq 50 years) as fixed effects in the model. For the analysis of change from baseline in \log_{10} (HBsAg) (IU/mL) by baseline HBeAg status, only treatment group and age (< 50 or \geq 50 years) will be included as fixed effects in the model.

In addition, the proportion of subjects in the FAS with HBV DNA < 20 IU/mL, the proportion of subjects with normal ALT by the central laboratory and 2018 AASLD criteria (ULN is 35 U/L for males and 25 U/L for females) using the M E approach, and the mean change from baseline in log10 (HBsAg) (IU/mL) and ALT (U/L) will be plotted with 95% CI over time using observed data from baseline to Week 96.

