FibroTest score will be summarized using descriptive statistics (sample size, mean, SD, median, Q1, Q3, minimum, and maximum) by treatment group for subjects in the FAS. The p-value, differences in change from baseline in FibroTest score between the 2 treatment groups and the associated 95% CI will be constructed using ANOVA models, including treatment group, baseline HBeAg status (HBeAg-positive or HBeAg-negative) and age (< 50 or ≥ 50 years) as fixed effects in the model. A shift table of fibrosis stage from baseline based on the FibroTest score at Week 24, 48, and 96 will be provided. Mean change from baseline in FibroTest score will be plotted with 95% CI over time using observed data from baseline to Week 96. A listing of fibrosis assessment by FibroTest will also be provided.

All the analyses of the secondary efficacy endpoints, using both the M F and the M E approach, and plots described above will be repeated for subjects in the Open-Label FAS from open-label baseline to Week 96. No statistical comparisons will be performed.

For subjects in the TFFU FAS, only HBV DNA, ALT, HBsAg, HBeAg loss/seroconversion, and HBsAg loss/seroconversion endpoints will be summarized by visit in the TFFU phase as described above only using the M E approach. No statistical comparisons will be performed.

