7.4.2. Serum Creatinine

For the renal safety analyses, observed creatinine values will be used.

For subjects in the Safety Analysis Set, the baseline and change from baseline in serum creatinine during the entire study period will be summarized using descriptive statistics. The baseline serum creatinine and change from baseline in serum creatinine will be compared between the 2 treatment groups using the two-sided Wilcoxon rank sum test.

For subjects in the Open-Label Safety Analysis Set, the open-label baseline and change from open-label baseline in serum creatinine during the open-label phase will be summarized using descriptive statistics. No statistical comparisons will be performed.

Median (Q1, Q3) and mean (95% CIs) of change from baseline to Week 96 in serum creatinine over time will be plotted by treatment group for subjects in the Safety Analysis Set. This will be repeated using subjects in the Open-Label Safety Analysis Set from open-label baseline to Week 96.

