7.5. Child-Pugh-Turcotte Score

The Child-Pugh-Turcotte (CPT) score is calculated as: the sum of the scores related to the 5 items in the table below (if any of the components are missing, the score is not calculated):

Measure	1 point	2 points	3 points
Total Bilirubin (mg/dL)	< 2	2 - 3	> 3
Serum Albumin (g/dL)	> 3.5	2.8 - 3.5	< 2.8
INR	< 1.7	1.7 - 2.3	> 2.3
Ascites	None	Slight/Moderate (medically controlled)	Severe (medically uncontrolled)
Hepatic Encephalopathy	None	Slight/Moderate (medically controlled)	Severe (medically uncontrolled)

For summary purposes, the score will be further classified into classes: Class A (5-6 points), Class B (7-9 points), and Class C (10-15 points). The number and proportion of subjects in each class of CPT score will be summarized in a shift table with baseline, Week 48, and Week 96 CPT class based on subjects in the Safety Analysis Set during the entire study treatment period. The distribution of the CPT class at these visits will be compared between the 2 treatment groups adjusting for baseline class using rank ANCOVA {LaVange 2008}.

The summaries described above will be repeated for subjects in the Open-Label Safety Analysis Set from open-label baseline to Week 96, using open-label baseline in place of baseline, and no statistical comparisons will be performed.

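### SAP 6.2.2 compares changes in FibroTest, log10 HBsAg and ALT without adjusting for the baseline value of the outcome, which gives away some precision at no benefit

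*SAP*

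**What the plan says.** For change in log10 HBsAg and in ALT, SAP 6.2.2 states that the p-value, the arm difference and its 95% CI "will be constructed using analysis of variance (ANOVA) models, including treatment group, baseline HBeAg status (HBeAg-positive or HBeAg-negative), and age" group as fixed effects. In the HBsAg analysis "by baseline HBeAg status, only treatment group and age" group remain. For FibroTest the corresponding quantities "will be constructed using ANOVA models, including treatment group, baseline HBeAg status (HBeAg-positive or HBeAg-negative) and age" group.

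SAP 6.2.1 lists "The change from baseline in fibrosis as assessed by FibroTest at Weeks 48 and 96" among the secondary efficacy endpoints. Changes in log10 HBsAg and in ALT are not on that list; the listed ALT endpoints are proportions.

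Protocol 8.6.2 has no baseline adjustment for continuous secondary endpoints either: "A Wilcoxon rank sum test may be used to compare the treatment groups, in an exploratory manner". The SAP does adjust for baseline in some categorical safety tables, for example Child-Pugh-Turcotte class in 7.5 ("adjusting for baseline class using rank ANCOVA"), BMD status in 7.3.1 and the UPCR and UACR categories in 7.4.6. No baseline-adjusted analysis of the three continuous changes is planned.

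**The concern.** The baseline value is available for every subject who contributes a change, because the change is computed from it. It is usually also a strong predictor of the change: subjects who start high tend to fall and those who start low tend to rise. A model that omits it leaves this predictable variation in the residual. It also lets a chance difference between the arms at baseline carry over in part to the estimated effect. The HBeAg and age-group terms remove only the portion of such a difference that lies between strata.

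At stake is the width of three sets of confidence intervals and how closely their point estimates can be trusted in this particular randomisation. Each comparison is to be reported with a p-value and a 95% CI, so it will be read as inference.

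**Working it through.** **The plan's own figures.** The documents give no SD, correlation, power or sample size for these three outcomes, so there is nothing of theirs to reproduce here. The stated 230 per arm belongs to the primary endpoint. It does reproduce (2.4% in both arms, 4% margin, one-sided 0.025: 230 per arm, power 80.03%) but does not depend on this point.

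**Inputs.** 230 per arm (SAP 1.3); model terms from SAP 6.2.2; the within-stratum correlation r between baseline and follow-up and the ratio of SDs are assumed.

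**Precision.** Let s0 and s1 be the within-stratum SDs at baseline and follow-up.

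- Change score: variance = s0² + s1² − 2·r·s0·s1
- Baseline-adjusted: variance = s1²·(1 − r²)
- Difference = s0² − 2·r·s0·s1 + r²·s1² = (s0 − r·s1)²

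The difference is never negative. It is zero only when r·s1 = s0, that is, when the slope r·s1/s0 equals 1. With s1 = s0 the ratio of change-score to adjusted variance is 2(1 − r)/(1 − r²) = 2/(1 + r), and interval width goes with its square root.

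**Imbalance.** If the arms differ by D at baseline, the change score subtracts D in full but follow-up carries only slope × D, so (slope − 1) × D remains. With 230 per arm the standard error of D is √(2/230) = 0.093 SD, so a chance imbalance at the 1.96-SE limit is 0.183 SD.

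| r (assumed, equal SDs) | Variance ratio 2/(1 + r) | Interval wider by | Effective sample size gained by adjusting | Share of D left (r − 1) | Size of remainder if D = 0.183 SD |
|---|---|---|---|---|---|
| 0.5 | 1.333 | 15.5% | 33% | −0.50 | 0.09 SD |
| 0.7 | 1.176 | 8.5% | 18% | −0.30 | 0.05 SD |
| 0.9 | 1.053 | 2.6% | 5% | −0.10 | 0.02 SD |

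**Simulation check** (460 subjects, two stratum factors, 1,500 runs per r). The ratio of adjusted to unadjusted standard error was 0.868, 0.924 and 0.976 at r = 0.5, 0.7 and 0.9, against 0.866, 0.922 and 0.975 from the formula. The unadjusted estimate moved with the baseline imbalance by −0.51, −0.28 and −0.09 per unit; the adjusted one stayed within about 0.02 of zero. Both estimators averaged close to zero over runs, as they should with no true effect.

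**Unequal SDs.** The gain can vanish. With s1 = 1.25·s0 and r = 0.8 the slope is 1.25 × 0.8 = 1. The change-score variance is 1 + 1.5625 − 2 = 0.5625·s0², and the adjusted variance is 1.5625 × 0.36 = 0.5625·s0². The gain can also be larger: with s1 = 0.85·s0 and r = 0.7 the adjusted interval is 0.832 times as wide, so the planned one is 1/0.832 − 1 = 20% wider.

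**Subgroup model.** If the 2:1 ratio of HBeAg-negative to HBeAg-positive subjects assumed in SAP 1.3 held, the HBeAg-positive HBsAg comparison would have about 230/3 ≈ 77 per arm. A 1.96-SE imbalance would then be 1.96 × √(2/77) = 0.32 SD, so the remainder is larger there than in the full set.

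**The case against.** The strongest reply is that nothing is broken. Change-score ANOVA in a randomised trial gives a valid test and an estimate that is unbiased over randomisations. Only FibroTest is a listed endpoint, it lies outside the testing sequence of Protocol 8.4, and the protocol treats comparisons of continuous secondary endpoints as exploratory. By Week 96 both arms have had 48 weeks of TAF. The correlations are unknown, and near 0.9 the cost is under 3% in width. The SAP covers the final analysis, written after the Week 48 analysis had been run (SAP 2.2), so replacing a model now could look post hoc and break continuity. All of this stands. It limits the importance of the point and shapes the remedy, but it gives no reason to prefer the unadjusted model.

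A reader might infer more than the documents support:

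- **That adjustment gains whenever the correlation is below 1.** It does not; a slope of 1 gives no gain even at r = 0.8. For ALT, equal SDs are doubtful from the plan itself, since SAP 3.6.3 takes the largest post-baseline value in a window but the last available baseline record.
- **That the whole chance imbalance stays in the estimate.** Only (slope − 1) of it does.
- **That ALT is worst affected because entry allows values up to 5 × ULN.** That is an eligibility ceiling. It says nothing about the spread or correlation of ALT in subjects already on TDF for at least 48 weeks.
- **That serum creatinine belongs here.** SAP 7.4.2 says "The baseline serum creatinine and change from baseline in serum creatinine will be compared between the 2 treatment groups", but by Wilcoxon rank sum test, to which the variance formula does not apply. The same pattern is used for eGFR (7.4.3), lipids and glucose (7.2.1.1) and TmP/GFR and FEPO₄ (7.4.7), and Protocol 8.7.1 itself specifies the Wilcoxon test for eGFR by Cockcroft-Gault at Week 48. The SAP uses rank ANCOVA only for categorical distributions. Changing creatinine alone would make it inconsistent with its neighbours.

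**Conclusion.** The point holds as one of efficiency and conditional bias. The three change analyses omit a covariate that is already collected and that, in large samples, cannot widen the interval. With equal SDs the planned intervals are about 15%, 8% or 3% wider than needed at r = 0.5, 0.7 or 0.9. Even a baseline imbalance at the 1.96-SE limit shifts the full-set estimate by only about 0.09 SD at r = 0.5 and 0.02 SD at r = 0.9. These sizes rest on assumed correlations and equal SDs; the true loss could be nil or somewhat larger.

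It would be wrong to read this as a type I error problem or as a threat to the trial's main results. No stated sample size or power depends on it, and the primary and key secondary conclusions are untouched.

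**What to change.** In SAP 6.2.2, add the continuous baseline value of the analysed outcome (FibroTest, log10 HBsAg or ALT) as a covariate beside treatment, baseline HBeAg status and age group. In the HBsAg model by HBeAg status, add baseline log10 HBsAg beside treatment and age group.

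If continuity with the completed Week 48 analysis is wanted, keep the planned ANOVA and report the adjusted model next to it, labelled as supplementary. The Week 48 SAP is a separate document, so whether it used the same models has to be checked there. SAP 1 already provides for changes after finalisation to be documented in the CSR.

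The cost is one covariate and one degree of freedom per model. No new data are needed. The real cost is timing: because Week 48 results exist, the addition should be dated and explained so that it is not taken for a choice driven by the data.

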3. STUDY DESIGN

3.1. Study Treatment Plan and Regimen

This is a randomized, double-blind, multicenter, active-controlled study to evaluate the safety and efficacy of TAF 25 mg QD in virologically suppressed subjects who switch from TDF to TAF compared to continued TDF treatment.

Approximately 460 subjects (with approximately 50% of subjects being \geq 50 years old) will be randomized in a 1:1 ratio (A:B) to receive either TAF 25 mg QD and matched placebo of TDF 300 mg QD or Gilead-provided TDF 300 mg QD and matched placebo of TAF 25 mg QD.

At randomization, subjects will be stratified by screening HBeAg status (HBeAg-negative vs. HBeAg-positive) and age (> 50 or < 50 years).

- Treatment Arm A: approximately 230 subjects administered TAF 25 mg QD and matched placebo of Tenofovir DF (TDF) 300 mg QD
- Treatment Arm B: approximately 230 subjects administered Gilead-provided TDF 300 mg QD and matched placebo of TAF 25 mg QD

The duration of double blind treatment is 48 weeks. All subjects who complete 48 weeks of treatment are eligible for participation in the open label TAF 25 mg extension period for an additional 48 weeks (through Week 96). During the double-blind period, subjects with a confirmed creatinine clearance by Cockcroft Gault Method (eGFR_{CG}) < 50 ml/min, and > 20% decline in eGFR by CKD-EPI (cystatin C) compared to baseline during the study, will be required to undergo dose modification to every other day dosing of study drug. Subjects with confirmed creatinine clearance < 30 mL/min during the double blind phase of the study will have the study drug permanently discontinued. Subjects with confirmed eGFR_{CG} < 50 mL/min will not undergo dose modification to every other day during the open-label TAF 25 mg extension period, nor will treatment be permanently discontinued for confirmed eGFR_{CG} < 30 mL/min during the open-label extension period.

Subjects who permanently discontinue study drug (either prematurely or at the end of study [Week 96]) for reasons other than HBsAg loss with confirmed seroconversion to anti-HBs will be followed every 4 weeks for 24 weeks off treatment or until initiation of appropriate alternative, HBV therapy, whichever occurs first. Use of appropriate, alternative HBV therapy is strongly encouraged.

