6.4.2. All Other Subjects Who Discontinue Study Drug

Subjects who have received at least one dose of study drug and permanently discontinue study drug for reasons other than HBsAg loss with confirmed seroconversion to anti-HBs will be followed every 4 weeks for 24 weeks off treatment or up to initiation of appropriate, alternative HBV therapy, whichever occurs first.

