7.5.5.2. Management of Exacerbation of Hepatitis in Subjects Who Have Discontinued Study Medication

If laboratory results indicate (1) an ALT elevation $> 2 \times$ baseline and $> 10 \times$ ULN alone OR associated with (2) abnormal laboratory parameters suggestive of worsening hepatic function (total bilirubin 2 \times baseline, INR 0.5 above baseline, provided both are > ULN) and the subject is on no post-study therapy for HBV, the following is recommended:

- Schedule the subject to return to the clinic as soon as possible (ideally no later than 3 days after the initial laboratory values were drawn). During the visit, perform a clinical assessment of the subject.
- Check the following laboratory parameters: serum ALT and AST, total bilirubin, INR, and albumin.
- If the ALT elevation is confirmed, the central clinical laboratory will conduct reflex testing for plasma HBV DNA, serology for HBV (HBsAg and HBsAb), HDV, HAV IgM, HCV and HEV. If Plasma HBV DNA is increasing, the investigator should consider immediate initiation of approved therapy.
- The subject should be followed until laboratory parameters (ALT, total bilirubin, INR) return to normal or baseline up to a maximum of 6 months after the initial occurrence of the event.

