3.1.7. TFFU Full Analysis Set

The TFFU FAS includes all randomized subjects who entered the TFFU period. Subjects will be analyzed according to the treatment to which they were randomized during the double-blind phase.

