7.2.2.3. Summaries of Laboratory Abnormalities

The following summaries (number and percentage of subjects) of laboratory abnormalities will be provided by treatment group (subjects categorized according to most severe abnormality grade) for (1) subjects in the Safety Analysis Set during the double-blind phase, (2) subjects in the Open-Label Safety Analysis Set during the open-label phase, and (3) subjects in the TFFU Safety Analysis Set during the TFFU phase:

- Treatment-emergent laboratory abnormalities
- Treatment-emergent Grade 3 and 4 laboratory abnormalities
- Treatment-emergent marked laboratory abnormalities (this will not be summarized for (3))

For all summaries of laboratory abnormalities, the denominator is the number of subjects with any nonmissing postbaseline (or open-label postbaseline, or post-TFFU baseline) value in the given study period. By-subject listings of Grade 3 or 4 and graded laboratory abnormalities will be provided by subject ID number and visit in chronological order.

7.2.3. **ALT Elevation**

An ALT elevation is defined as serum ALT $> 2 \times$ open-label baseline value and $> 10 \times$ ULN, with or without associated symptoms. Confirmed ALT elevation (ALT flare) is defined as ALT elevations at 2 consecutive open-label postbaseline visits. All treatment-emergent ALT elevations including confirmed ALT elevations will be summarized for the open-label phase only. All treatment-emergent and nontreatment-emergent ALT elevations will be included in a listing.

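### Off-treatment HBV DNA is summarised by visit with Missing = Excluded only, although follow-up can end because of relapse; add a cumulative measure over all entrants and show therapy starts by visit

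*SAP*

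**What the plan says.** **Analysis rule.** SAP 6.2.2 limits the TFFU efficacy summary to HBV DNA, ALT, HBsAg, and HBeAg and HBsAg loss or seroconversion. These "will be summarized by visit in the TFFU phase as described above only using the M E approach", with no treatment comparison. The same section defines the rule: "In the M E approach, all missing data will be excluded in the computation". For the FAS and the Open-Label FAS, proportion endpoints are by default also analysed with Missing = Failure, where "all missing data will be treated as failures and included in both the numerator and denominator". TFFU gets one rule and no sensitivity analysis.

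**Population.** SAP 3.1.7: "The TFFU FAS includes all randomized subjects who entered the TFFU period".

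**End of follow-up.** Under Protocol 6.4.2, subjects who stop for reasons other than HBsAg loss with confirmed seroconversion are "followed every 4 weeks for 24 weeks off treatment or up to initiation of appropriate, alternative HBV therapy, whichever occurs first". Seroconverters follow a separate schedule (Protocol 6.4.1) with no such end point.

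**Reasons for starting therapy.** Protocol 7.5.5.2 covers subjects off study drug whose ALT exceeds both 2 times baseline and 10 times ULN. Once that is confirmed, HBV DNA is reflex-tested: "If Plasma HBV DNA is increasing, the investigator should consider immediate initiation of approved therapy". Separately, Protocol 3.1 says of all non-seroconverters who stop: "Use of appropriate, alternative HBV therapy is strongly encouraged".

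**ALT.** SAP 7.2.3: "All treatment-emergent ALT elevations including confirmed ALT elevations will be summarized for the open-label phase only". However, SAP 7.2 and 7.2.2.3 tabulate graded laboratory abnormalities by worst grade over the TFFU phase.

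**The concern.** A Missing = Excluded proportion at a visit describes the subjects still observed at that visit. When the outcome can itself cause departure, those subjects are a selected group. Here a relapser may start therapy, which ends follow-up and removes that subject from every later visit. A reader who takes the Follow-Up Week 24 column as the share of entrants who stay suppressed after stopping could then be misled.

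HBV DNA is where this matters most. It is not in the laboratory grading scale (Protocol Appendix 4), so the worst-grade TFFU tables cannot show viral relapse, and SAP 7 plans no by-visit TFFU safety summaries. The SAP 6.2.2 table is the only planned summary of viral relapse off treatment; the rest is listings. SAP 4.1 counts subjects who began other HBV therapy, but once overall and in the Safety Analysis Set. It therefore does not show how the TFFU denominator shrank from visit to visit.

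**Working it through.** The plan states no figure for the TFFU summaries, so there is none to reproduce. The check is of the mechanism, with assumed inputs.

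**From the documents:** six follow-up visits at 4-week intervals (Protocol 6.4.2; SAP Table 3-7); follow-up ends at other therapy; missing values are excluded.

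**Assumed, not from the documents:**
- 100 subjects enter.
- True cumulative relapse (HBV DNA >= 20 IU/mL) by 24 weeks is C = 30%, 60% or 90%, at a constant hazard.
- Relapse persists until therapy starts.
- Before the next visit, a relapsed subject starts therapy with probability qr and a non-relapsed subject with probability qn.

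**Formulas.** The hazard per interval is h = 1 - (1 - C)^(1/6). At each visit, h x N subjects move from the non-relapsed N to the relapsed R. The table reports R/(R + N). Then R becomes (1 - qr)R and N becomes (1 - qn)N.

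**Worked case, C = 60%, qr = 0.5, qn = 0.** h = 1 - 0.4^(1/6) = 0.142.
- Visit 1: R = 14.2, N = 85.8, reported 14.2%.
- Visit 3: reported 24.1%.
- Visit 6: N = 40.0 and 55.2 subjects remain, so R = 15.2 and the table reports 15.2/55.2 = 27.5%, against a true 60%.

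**Follow-Up Week 24, C = 60%:**

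| qr | qn | Missing = Excluded, % >= 20 IU/mL | Subjects in column | Missing = Failure, % | Ever >= 20 IU/mL before therapy, % of all entrants |
|---|---|---|---|---|---|
| 0 | 0 | 60.0 | 100.0 | 60.0 | 60.0 |
| 0.2 | 0.2 | 60.0 | 32.8 | 86.9 | 40.5 |
| 0.5 | 0.2 | 34.1 | 19.9 | 86.9 | 40.5 |
| 0.5 | 0 | 27.5 | 55.2 | 60.0 | 60.0 |
| 1 | 0 | 14.2 | 46.6 | 60.0 | 60.0 |
| 0.2 | 0.5 | 88.7 | 11.0 | 98.8 | 24.7 |

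For C = 30% and 90%, Missing = Excluded gives 14% and 70% (qr 0.5, qn 0.2), 11% and 60% (0.5, 0), 6% and 32% (1, 0), and 67% and 98% (0.2, 0.5).

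**What this shows.**
1. The direction depends on who leaves faster. Equal rates give no bias; faster departure of non-relapsers reverses it.
2. Missing = Failure is not a clean repair. It is right when only relapsers leave, but counts every other departure as relapse: 86.9% against 60% when qn = 0.2.
3. The last column does not depend on qr, so early departure after relapse cannot distort it. It does fall as qn rises, so it must be read beside therapy starts. In the third row, 40.5% relapsed first, 100 x 0.4 x 0.8^5 = 13.1% remained untreated and suppressed, and 100 - 40.5 - 13.1 = 46.4% started therapy with no measured relapse.

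**The case against.** **The direction is not established.** Therapy is encouraged for every non-seroconverter who stops, and in the on-treatment ALT-flare setting Protocol 7.5.5.1 directs subjects with bridging fibrosis or cirrhosis to commercial therapy once study drug stops. Many departures may have nothing to do with off-treatment HBV DNA. Nor does the protocol name HBV DNA >= 20 IU/mL alone as a reason to start therapy; Protocol 7.5.5.2 applies after a confirmed ALT elevation. This stands. A reader might infer that withdrawal will certainly look safer than it is, or that every subject who leaves is viremic. The documents support neither.

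**ALT is largely covered.** A reader might infer from SAP 7.2.3 that post-treatment ALT elevations are only listed. They are not: SAP 7.2.2.3 tabulates worst-grade and Grade 3-4 abnormalities over TFFU, and Grade 4 ALT is > 10 x ULN (Protocol Appendix 4). With TFFU baseline ALT at or below 5 x ULN, such a value necessarily exceeds 2 x baseline, because 2 x 5 = 10. A subject who flares and then starts therapy stays in that cumulative count. SAP 7.1.7 also summarises post-treatment AEs, Grade 3-4 AEs and SAEs. Only the combined ALT definition, with confirmation and timing, is missing.

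**The tables are descriptive.** No stated objective or endpoint concerns TFFU, no comparison is made, and all TFFU efficacy data are listed (SAP 6). This limits the importance of the point. It does not remove it, because listings do not give a relapse proportion and the one summary that does can mislead.

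**Conclusion.** The point holds for HBV DNA. Missing = Excluded by visit is the only planned rule, departure can depend on relapse, and no cumulative off-treatment HBV DNA measure is planned. Later-visit suppression is likely, not certain, to be overstated. The size cannot be fixed from the documents: with 60% true relapse, the illustration gives 14% to 34% shown when relapsers leave sooner, 60% at equal rates, and 89% when non-relapsers leave faster. Those figures rest on assumed hazards and departure rates and on relapse persisting until therapy. They also set a by-visit proportion against a cumulative one, and the two coincide only under that persistence assumption with no selective departure. The planned table cannot tell a reader which case applies, and that is the main reason to change it. For ALT the gap is small. Primary and key secondary results do not depend on any of this.

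**What to change.** In SAP 6.2.2, for the TFFU FAS:

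1. Add the number and percentage of all TFFU entrants with HBV DNA >= 20 IU/mL at any time before alternative HBV therapy. Give the cumulative incidence with therapy start as a competing event, or a composite of relapse and therapy start. Do not use Kaplan-Meier censored at therapy start: it assumes that subjects who start therapy without measured relapse have the same later risk as those still untreated, which these data cannot check.
2. Beside the Missing = Excluded columns, show at each visit the number still untreated and observed and the cumulative number who have started other HBV therapy. Label the table *among subjects still untreated and observed*.

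Optionally, extend the SAP 7.2.3 ALT-elevation summary to TFFU, using TFFU baseline.

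**Cost.** One or two descriptive tables. HBV DNA is already collected at follow-up visits (Protocol 6.4.3), and starting other therapy is already counted (SAP 4.1); the by-visit counts also need the start date, so its capture should be confirmed. The off-treatment picture may look less favourable. If the SAP is already final, the addition can be documented in the clinical study report, as SAP 1 provides.
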